### 11.3.3. Reporting Procedures

The investigator shall submit to the sponsor and to its representative all associated information and documentation related to each AE. Notification to local authorities should follow local requirements.

AEs will be categorized according to severity and relatedness.

#### Adverse Event Severity Classification

 Neurolief Brain Innovation	MOOD: CLINICAL INVESTIGATION PLAN	Doc No.: CL-CIP-201 Rev: REV.3 / 09June2021 Pg. 64 of 92
--	--	--

Severity of AEs will be determined using the following scale:

- Mild: The subject is aware of a sign or symptom, but it is easily tolerated.
- Moderate: Discomfort or interference with usual activity.
- Severe: Incapacitating, with inability to engage in usual activity.

**Relatedness:** The investigator will determine the relationship of each adverse event to the use of the device / procedure.

*Adverse Event Relationship Classification*

Causality assessments define the relationship between the use of the medical device (including the medical procedure) and the occurrence of each adverse event. During causality assessment activity, clinical judgment shall be used and the relevant documents, such as the Clinical Evaluation Report and the Risk Management Report shall be consulted, as all the foreseeable serious adverse events and the potential risks are listed and assessed there. The presence of confounding factors, such as concomitant medication/treatment, the natural history of the underlying disease, other concurrent illness or risk factors shall also be considered.

Each AE will be classified according to five different levels of causality. The Sponsor and the Investigators will use the following definitions to assess the relationship of the serious adverse event to the medical device or procedures:

Relationship to study product administration will be determined as follows:

**Not related:** relationship to the device or procedures can be excluded when:

- the event is not a known side effect of the product category the device belongs to or of similar devices and procedures;
- the event has no temporal relationship with the use of the device or the procedures;
- the serious event does not follow a known response pattern to the medical device (if the response pattern is previously known) and is biologically implausible;
- the discontinuation of medical device application or the reduction of the level of activation/exposure - when clinically feasible – and reintroduction of its use (or increase of the level of activation/exposure), do not impact on the serious event;
- the event involves a body-site, or an organ not expected to be affected by the device or procedure;
- the serious event can be attributed to another cause (e.g. an underlying or concurrent illness/ clinical condition, an effect of another device, drug, treatment or other risk factors);
- the event does not depend on a false result given by the device used for diagnosis, when applicable;
- harms to the subject are not clearly due to use error;
- In order to establish the non-relatedness, not all the criteria listed above might be met at the same time, depending on the type of device/procedures and the serious event.

 Neurolief Brain Innovation	MOOD: CLINICAL INVESTIGATION PLAN	Doc No.: CL-CIP-201 Rev: REV.3 / 09June2021 Pg. 65 of 92
--	--	--

**Unlikely:** the relationship with the use of the device seems not relevant and/or the event can be reasonably explained by another cause, but additional information may be obtained.

**Possible:** the relationship with the use of the device is weak but cannot be ruled out completely. Alternative causes are also possible (e.g. an underlying or concurrent illness/ clinical condition or/and an effect of another device, drug or treatment). Cases where relatedness cannot be assessed or no information has been obtained should also be classified as possible.

**Probable:** the relationship with the use of the device seems relevant and/or the event cannot reasonably be explained by another cause, but additional information may be obtained.

**Causal relationship:** the serious event is associated with the device or with procedures beyond reasonable doubt when:

- the event is a known side effect of the product category the device belongs to or of similar devices and procedures;
- the event has a temporal relationship with device use/application or procedures;
- the event involves a body-site or organ that
  - the device or procedures are applied to;
  - the device or procedures have an effect on;
- the serious event follows a known response pattern to the medical device (if the response pattern is previously known);
- the discontinuation of medical device application (or reduction of the level of activation/exposure) and reintroduction of its use (or increase of the level of activation/exposure), impact on the serious event (when clinically feasible);
- other possible causes (e.g. an underlying or concurrent illness/ clinical condition or/and an effect of another device, drug or treatment) have been adequately ruled out;
- harm to the subject is due to error in use;
- the event depends on a false result given by the device used for diagnosis, when applicable;
- In order to establish the relatedness, not all the criteria listed above might be met at the same time, depending on the type of device/procedures and the serious event.

The Sponsor and the Investigators will distinguish between the AEs related to the device and those related to the procedures (any procedure specific to the clinical investigation). An adverse event can be related both to procedures and the device. Complications of procedures are considered not related if the said procedures would have been applied to the subjects also in the absence of device use/application.

In some particular cases the event may be not adequately assessed because information is insufficient or contradictory and/or the data cannot be verified or supplemented. The Sponsor and the Investigators will make the maximum effort to define and categorize the event and avoid these situations. Where the

Sponsor remains uncertain about classifying the serious event, it should not exclude the relatedness and classify the event as “possible”.

**Adverse Event Outcome Classification**

Adverse Event Outcome Classification will be defined according to the following:

**Resolved:** The event has fully resolved at the end of the study.

**Resolved with sequel:** The event has resolved, but retained pathological conditions resulting from the prior disease or injury.

**Continuing:** The event is ongoing at the end of the study.

**Death:** This event is determined to be the cause of death.

#### **11.3.4. Reporting of Adverse Events**

Please refer to **Table 2** for a list of the minimum AE reporting requirements for Investigators. If local regulations or IRB/EC require faster reporting, then the Investigator will adhere to those requirements. Reporting of all safety events to the Sponsor will be completed through Investigator submission of the AE CRF by e-mail and/or eCRF in the remote data capture (RDC) system. In case of emergency only for SAEs (ex. RDC system is unavailable), the sponsor site representative may be contacted directly; this will not serve as a substitute for proper reporting on the appropriate eCRF.

**Table 2: AE Reporting Requirements**

Type	Report to	Reporting Timeframe (from time of learning of event)
Adverse Event (AE)	Sponsor	Within 10 working days
	IRB/EC	Per EC reporting requirements
Serious Adverse Event (SAE)	Sponsor	Within 24 hours
	IRB/EC	Per/IRB/ EC reporting requirements
Adverse Device Effect (ADE), Serious Adverse Device Effect (SADE) and Unanticipated Serious Adverse Device Effect (USADE/UADE)	Sponsor	Within 24 hours
	IRB/EC	Per EC reporting requirements
	Sponsor	Within 48 hours

Type	Report to	Reporting Timeframe (from time of learning of event)
Device Deficiency	IRB/EC	If SAE occurs due to the device deficiency, within 24 hours of learning of the event and per EC reporting requirements
	EC	Per EC reporting requirements

Events will be reviewed by the Sponsor to determine any reporting obligations to the FDA or Regulatory Authorities as well as IRB/EC. Reporting will occur within the timelines per local regulations and requirements. The Principle Investigator is responsible to report the events to the IRB/EC.

The sponsor shall immediately conduct an evaluation of any unanticipated events if determines that the event presents an unreasonable risk to subjects, report the results of such evaluation to the Regulatory authority and to reviewing IRB/EC and participating investigators within 10 working days after the sponsor first receives notice of the event.

### **11.3.5. Notification to Authorities**

The following events are generally considered reportable during the course of this study and should be reported to the Sponsor:

- any SAE
- any Device Deficiency that might have led to an SAE if
  - suitable action had not been taken or
  - intervention had not been made or
  - if circumstances had been less fortunate
- new findings/updates in relation to already reported events.
- deaths

Events will be reviewed by the Sponsor for reporting obligations to Regulatory Authorities. Reporting to the sponsor or its designated CRO is responsible for relaying adequate information on reportable events to the regulatory authorities per country's applicable reporting requirements.

### **11.3.6. Device Deficiencies**

Device deficiency is an inadequacy with respect to the device's identity, quality, durability, reliability, usability, safety, or performance, such as a malfunction, failure, use error and inadequacy in the information supplied by the manufacturer including labeling. Device deficiencies may or may not be associated with an adverse event.

 Neurolief Brain Innovation	MOOD: CLINICAL INVESTIGATION PLAN	Doc No.: CL-CIP-201 Rev: REV.3 / 09June2021 Pg. 68 of 92
--	--	--

All device deficiencies will be entered in the eCRF. Device deficiencies that were associated with an SAE or that could have led to an SAE if a) suitable action had not been taken or b) intervention had not been made or c) if circumstance had been less fortunate, will be documented within **24 hours** of knowledge. If possible, the device(s) associated with a malfunction or failure should be retained until arrangements for its collection are made by Neurolief.

Device deficiencies are NOT to be reported as AEs. However, if there is an AE that results from a device deficiency, that specific event would be recorded on the appropriate eCRF.

A device deficiency must be reported to Neurolief (technical support) within 48 hours after the investigator is made aware of the event.

Device deficiencies will be summarized and reported in the clinical study report and will be reported to the regulatory authorities per country's applicable reporting requirements.

### **11.3.7. Safety Monitoring and Adjudication of Adverse Events**

The sponsor will review submitted AE information and may request supplemental information if needed. For SAE, U(SA)DE and ADE (as classified by the investigator) a narrative will be prepared and adjudicated for assessing the relatedness, seriousness and possible action items required. The sponsor may ask for further information or clarification from the investigator. A summary of the adjudication results will be issued; if different than investigator's report, PI will be notified, and the information will be forwarded to Neurolief medical advisor for final adjudication. All the safety data including any adverse events or side effects related to the treatment will be reported periodically to the independent data monitoring committee (DMC) as indicated in section 14.1. The DMC will provide recommendations to sponsor about stopping or continuing the trial or making modifications to enhance safety of trial participants to protect the integrity of the study.

Adjudicated events will serve as a basis for reporting AE/SAE. Differences between site-reported events and adjudicated events will also be presented and discussed in the report.

 Neurolief Brain Innovation	MOOD: CLINICAL INVESTIGATION PLAN	Doc No.: CL-CIP-201 Rev: REV.3 / 09June2021 Pg. 69 of 92
--	--	--

## 12. Statistical Considerations

### 12.1. Study Design and Objectives

#### 12.1.1. Objectives

The MOOD Study will evaluate the safety and efficacy of a self-administered treatment for MDD using an external combined occipital and trigeminal nerve stimulator device (Relivion®DP).

#### 12.1.2. Study Design

This is a prospective, randomized, double-blind, parallel-group, sham controlled, multi-center clinical investigation followed by an active open label extension period. All enrolled patients are those treated with the Relivion®DP device either by active treatment or sham treatment. The treatment will be done according to the IFU. Patients duration in the study will be up to 20 weeks (including the screening period).

One interim analysis is planned after 86 (~80% of the calculated sample size) evaluable subjects have been accrued, mainly for sample size re-assessment. The primary, as well as the safety endpoints will be assessed in the ITT, mITT, PP and mYITT analysis sets.

After the last treated patient will complete full study duration, a final clinical study report will be generated with conclusions relating back to original objective(s) and hypothesis/hypotheses.

### 12.2. Study Endpoint Variables

#### 12.2.1. Primary endpoint variable

The primary endpoint is the change in HDRS17 total score from baseline to 8 weeks post treatment initiation, in each of the study groups. This variable will be calculated by subtracting the subject's baseline HDRS17 score from the score at visit 4.

#### 12.2.2. Secondary and exploratory endpoint variables

The secondary endpoints of responder and remission will be represented in the form of binary variables which will be assigned the value of "1" if the subject is a "responder" or a "remitter" per specific secondary endpoint, and "0" otherwise. Other exploratory binary endpoints will be defined in a similar manner.

Secondary and exploratory endpoints described as changes from baseline, such as QIDS-SR-16, CGI-S and CGI-I and MDRS will be calculated by subtracting the subject's baseline score from the score at each visit.

 Neurolief Brain Innovation	MOOD: CLINICAL INVESTIGATION PLAN	Doc No.: CL-CIP-201 Rev: REV.3 / 09June2021 Pg. 70 of 92
--	--	--

### 12.2.3. Safety endpoint variables

Incidence of all adverse events and complications by severity and relationship to study device.

## 12.3. Study Hypothesis

Null hypothesis:

Mean change from baseline in HDRS17 total score to 8 weeks post treatment initiation in subjects suffering from Major Depressive Disorder (MDD) in the active Relivion®DP arm = Mean change from baseline in HDRS17 to 8 weeks post treatment initiation in the sham arm.

Alternative hypothesis:

Mean change from baseline in HDRS17 total score to 8 weeks post treatment initiation in subjects suffering from Major Depressive Disorder (MDD) in the active Relivion®DP arm ≠ Mean change from baseline in HDRS17 to 8 weeks post treatment initiation in the sham arm.

## 12.4. Sample Size Estimation

Sample size estimation is driven by the hypothesis testing of the primary endpoint and will be calculated using the sample size equation for a two-sample t-test, even though for the final analysis we may employ a statistically more powerful model such as repeated measures ANOVA.

An effect size of 0.5 (Cohen's d- Cohen, J. (1988). Statistical power analysis for the behavioral sciences (2nd ed.) Hillsdale, NJ: Lawrence Earlbaum Associates.) is considered a moderate effect size, and is lower than effect sizes seen for similar studies, thus 0.55 will be considered in this study for sample size estimation as the minimally important clinical effect size to be detected.

In a company feasibility study of the Relivion®DP device we evaluated the mean change from baseline up to weeks 3 and 6 in HDRS-17 score. The 3 week results were a (baseline adjusted) mean change of -5.95 points (95% CI:[-8.1,-3.8]) and the standard deviation of 4.2 points. The 6 week results were a (baseline adjusted) mean change of -8.4 points (95% CI:[-10.6,-6.26]) and the standard deviation of 5.6 points. This study had no control arm thus considering a minimally important effect size (Cohen's D) of 0.5 (and assuming equal group variances rounded up to 5 and 6 at 3 and 6 weeks respectively) we would expect an HDRS17 score reduction in the sham group of about 3.45 points at 3 weeks and 5.4 points at 6 weeks unless the treatment arm has a greater reduction.

In planning their study, Levkovitz et al (Brainsway Ltd.) assumed that effect size of 0.5 and a difference of 3.75 points between active to sham subjects treated with TMS will provide a significant clinical effect. The final results show a significant reduction in HDRS21 of 6.39 points in the TMS group compared to 3.28 in the sham group with an effect size of 0.76. Neuronetics Inc. reported an HDRS17 score reduction of 5.2 points in the active TMS group compared with a 3.3 point reduction in the sham group (ES>0.5), with a

 Neurolief Brain Innovation	MOOD: CLINICAL INVESTIGATION PLAN	Doc No.: CL-CIP-201 Rev: REV.3 / 09June2021 Pg. 71 of 92
--	--	--

minimal considered effect size of 0.4. Moreover, in a large analysis of the FDA database of antidepressant medications, Khan et al reported that the mean percentage reduction from the baseline in HDRS17 score was 40.7% for active treatment and 30.9% for placebo.

We use conservative estimates of a 3.3-point difference with a standard deviation of 6 points. Calculations show that a sample size of 53 subjects per group (total 106) would provide 80% power at a 5% level of significance (two-sided) to detect the difference between treatment and sham groups.

Given our preliminary results, together with other companies clinically relevant data, we hypothesize that our statistical assumptions are aligned with competitive treatments for MDD.

The company anticipates that after randomization, but before the endpoint can be observed, up to 15% of the subjects will drop out from the study irrespective of study arm and success of treatment; thus, an adjustment for this drop-out rate is made and a sample size of 124 is required at the point of randomization.

We shall randomize an additional up to 36 subjects (30+15% dropout) in the age range 18-21 to assess efficacy in this age range as well.

## 12.5. Interim Analysis

Planning one interim analysis that permits an increase in the sample size as described below does not additionally inflate the type I error [38]–[41]. In addition, the final analysis is performed using the conventional test as appropriate for the statistical hypothesis.

An interim analysis will be performed by an independent statistician once about 80% of the required number of subjects aged 22-70 have been randomized and completed the 8-week post treatment initiation visit. Depending on the outcome of the interim analysis, the study will either continue to the originally planned sample size, stop for futility, stop for efficacy, or continue with an increased sample size. These decisions will be made based on the conditional power (CP), which is defined as the conditional probability that the result will exceed a critical value at the interim given the observed effect size.

Note that the interim analysis will be conducted on the ITT, mITT, PP and mYITT analysis sets, and the study will be stopped due to futility only if the interim effects in all populations fall below the CP threshold.

### 12.5.1. Procedure

After all the relevant data will be entered into the database, and the database cleaned, a soft lock to the database will be performed. An independent un-blinded statistician (not the study statistician) will perform the assessments described below. A designated data monitoring team will recommend whether to stop the study once the interim results are available.

 Neurolief Brain Innovation	MOOD: CLINICAL INVESTIGATION PLAN	Doc No.: CL-CIP-201 Rev: REV.3 / 09June2021 Pg. 72 of 92
--	--	--

At the interim analysis, the data of the evaluable subjects in the ITT, mITT, PP and mYITT sets will be analyzed.

### 12.5.2. Blinding

Only the unblinded statistician and members of the data monitoring committee (DMC) will be exposed to the interim report. The members of the data monitoring team may also have access to the unmasked information of the interim analysis. Investigators and company directors will only be informed of a decision to continue or to discontinue the trial, or to implement modifications in trial procedure. The unblinded statistician who is responsible for conducting the interim analyses should ensure that the unmasked data is not available to any unauthorized person within or outside the company.

### 12.5.3. Decision Rules

The study will either continue to the originally planned sample size if the result is “favorable”, stop for futility if the result is “unfavorable”, stop for success if the result is “overwhelming” or an increase will be made to the sample size if the result is “promising”. These decisions will be made based on the conditional power (CP), defined as the conditional probability that the result will exceed a critical value at the interim given the observed effect size  $\widehat{\delta}_1$  = difference between mean change in HDRS17 scores for the active versus sham groups at the interim look.

Notation:

n1= sample size at interim analysis.

n2= original sample size calculated based on assumed effect size.

nmax = the highest sample size the company is willing to use, nmax = 250 subjects and is based on a more conservative estimate of the effect size of 0.356.

CPmin= is the calculated minimum CP based on the ratios nmax/n2, n1/n2 and the target study power (80%).

The following are the decision rules for the interim analysis which will be performed upon accrual of ~80% of the sample size, 86 evaluable subjects:

- If the result is “Unfavorable”, i.e.  $CP < CP_{min} = 29.14\%$  (interim result is so disappointing that it is not worth increasing the sample size to retrieve conditional power), then stop the trial for futility.
- If the result is “Promising”, i.e.  $29.14\% \leq CP < 80\%$  the sample size is increased recover the targeted power of 80%. The sample size used will be either the new calculated sample size based on the conditional power (as described in Sample size re calculation using conditional power Jonathan S. Denne Statist. Med. 2001; 20:2645–2660) or the predetermined maximum sample size of 250 subjects.

 Neurolief Brain Innovation	MOOD: CLINICAL INVESTIGATION PLAN	Doc No.: CL-CIP-201 Rev: REV.3 / 09June2021 Pg. 73 of 92
--	--	--

- If the result is “Favorable”, i.e. CP  $\geq$  80% the interim results are sufficiently favorable, and the trial continues to the original sample size planned of 106 (before allowance for dropouts) without the need to adaptively increase the sample size.
- If the result is “overwhelming” i.e. primary endpoint at the interim analysis is statistically significant at a 0.04108 level of significance, then stop the study for success. This was calculated based on an adaptive design with one interim analysis planned to either stop the study for futility or early success at the interim with a Lan-DeMets alpha spending approach using a Pocock type function, where at the interim the study will be stopped for success if the null hypothesis is rejected at an alpha level of 0.04108.

Note that the interim analysis will be conducted on all populations (ITT, mITT, PP and mYITT analysis sets, see **Section 12.7**), and the study will be stopped due to futility only if the interim effects in all populations fall below the threshold.

The un-blinded statistician will also calculate the sample size required to test the null hypothesis to achieve 80% power at 4.108% level of significance given the current trend.

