#### **12.5.4. Controlling the Alpha Level for the Primary Endpoint**

The overall alpha level for this study is 5%. According to [Müller 2001; Jonathan 2001 Broberg 2013 and Siu 2001], planning an interim analysis that permits an increase in the sample size as described above does not inflate the type I error.

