#### **12.7.5. Statistical Analysis of Analysis Sets**

Safety assessments will be performed on the ITT and mYITT analysis set.

The mITT cohort will serve as the principal data analysis set for the primary and secondary statistical evaluation of the efficacy endpoints. The primary, secondary and exploratory efficacy assessment will also be performed on the per protocol (PP) analysis set as a sensitivity analysis and to show consistency of study results. The primary and secondary efficacy analyses will also be performed on the mYITT analysis set.

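### Protocol 12.5.3 sends the same interim result both to continuation and to a stop for success, and the final test stays at 0.05 without accounting for that stop

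*Protocol*

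**What the plan says.** Protocol 12.5.3 sets four outcomes for one look at 86 evaluable subjects. CP is computed at the observed effect.

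- CP below 29.14% is Unfavorable: stop for futility.
- CP from 29.14% to below 80% is Promising: enlarge, up to 250.
- CP of 80% or more is Favorable: "the interim results are sufficiently favorable, and the trial continues to the original sample size planned of 106".
- Overwhelming: if the "primary endpoint at the interim analysis is statistically significant at a 0.04108 level of significance, then stop the study for success". This level is said to have been derived "with a Lan-DeMets alpha spending approach using a Pocock type function".

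The interim is run on four analysis sets (ITT, mITT, PP, mYITT). A rule for combining them is given for futility only: "the study will be stopped due to futility only if the interim effects in all populations fall below the threshold". Protocol 12.7.5 makes mITT the principal efficacy set in general ("The mITT cohort will serve as the principal data analysis set for the primary and secondary statistical evaluation of the efficacy endpoints") but does not mention the interim decisions.

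On error control, Protocol 12.5 states that "the final analysis is performed using the conventional test as appropriate for the statistical hypothesis", and 12.5.4 that "planning an interim analysis that permits an increase in the sample size as described above does not inflate the type I error". Protocol 12.8.2 and SAP 9.1 list the early efficacy test as an exception to the 5% level and set no matching final level. Protocol 12.9.1 and SAP 11.5.1 both judge the final primary test at p < 0.05. Protocol 12.5.3 also asks the unblinded statistician for the sample size to "achieve 80% power at 4.108% level of significance given the current trend".

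SAP 2.2.1 reports that the interim was Favorable and that enrolment continued to the original 124. It names no analysis set.

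**The concern.** A CP of 80% at a late look already requires strong interim evidence. If it requires stronger evidence than p = 0.04108, the Favorable zone lies wholly inside the stop-for-success zone. The rules then give opposite instructions for the results the design most expects.

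This also bears on the final test. A usable efficacy stop spends alpha, so a later test at an unadjusted 0.05 can take the total above the stated 5%. If no efficacy claim was available at the interim, 0.05 is sound. The correct level for the primary test of a pivotal trial therefore depends on a precedence that the documents do not state.

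**Working it through.** **Inputs.** n1 = 86, n2 = 106, nmax = 250, CP at the observed effect, stop level 0.04108 two-sided (z = 2.0427), all from Protocol 12.5.3. Difference 3.3, SD 6 and two-sided 5%, from Protocol 12.4. Information fraction t = 86/106 = 0.8113, so √t = 0.9007 and √(1−t) = 0.4344.

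**Reproducing the plan's futility threshold.** Take CPmin as the smallest CP at which the unadjusted 1.96 test at N = 250 stays conservative. This solves

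[√((250−86)/(106−86))·(1.96√106 − z√86) + z√86]/√250 = 1.96,

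giving z = 1.550. Then CP = Φ((1.550/0.9007 − 1.96)/0.4344) = 29.13%, against 29.14% stated. With 2.0427 in place of 1.96 the equation gives 28.3%. The CP scale therefore rests on 86, 106 and 1.96.

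**Favorable against stop.**

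- CP(z) = Φ((z/√t − 1.96)/√(1−t)).
- CP = 80% at z = 0.9007 × (1.96 + 0.8416 × 0.4344) = 2.095, so p = 0.0362 (0.0392 if referred to t with 84 df).
- At the stop boundary, z = 2.0427 gives CP = 76.1% (78.5% on t).
- In HDRS17 points, the standard error is 6√(2/43) = 1.294. The stop needs 2.0427 × 1.294 = 2.64 and Favorable needs 2.095 × 1.294 = 2.71.

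Every Favorable result also meets the stop rule. Results with CP from 76.1% to 80% are told both to enlarge and to stop.

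**How often.** Under 3.3 points and SD 6, mean Z = 3.3/1.294 = 2.55. P(Z > 2.0427) = 69.4%, all of it in the zone where two rules apply (68.3% on t).

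**The stated boundary.** Pocock-type spending is 0.05·ln(1 + (e−1)t). It gives 0.0436 at t = 0.8113 and 0.0432 at t = 0.80. The stated 0.04108 needs t ≈ 0.7415, roughly 86 of 116.

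**False success under the null.** Success requires the active arm to be better, so the benchmark is 2.5% one-sided. With the stop first, the error is P(Z > 2.0427) = 2.05% plus the integral, over continuing z, of φ(z)·[1 − Φ((1.96 − z√(86/N))/√(1 − 86/N))]. One analysis set is used throughout.

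| Rule in force, final test at 1.96 | Futility followed | Not followed |
|---|---|---|
| Stop first, Promising sized to CP 80%, cap 250 | 2.71% | 3.07% |
| Stop first, Promising always 250 | 2.56% | 2.92% |
| Stop first, N fixed at 106 | 2.87% | 3.23% |
| Continue first, Promising sized to CP 80% | 1.97% | 2.33% |
| Continue first, Promising always 250 | 1.78% | 2.14% |

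**Final two-sided level that holds 2.5% one-sided, stop first.** With futility followed / not followed: 0.033 / 0.027 (sized to CP 80%) and 0.043 / 0.030 (always 250). With N fixed at 106 and no futility stop: 0.028.

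**The case against.** The arithmetic is not disputed; the objections concern weight and reach.

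- **The excess is modest.** With the rules followed on one set and the stop first, error is 2.56–2.71%. This stands, though futility requires all four sets to fail, so giving full credit for a one-set futility stop is optimistic.
- **Containment is fragile.** It disappears at about 76 or fewer evaluable of 106 on the normal scale, and at about 82 or fewer on the t scale. The planned model adjusts for baseline and center, and the four sets differ in size. This stands as a limit. The missing precedence and missing final level do not depend on full containment.
- **The report of Favorable suggests that continuation ruled.** That is plausible: with the stop first, the Favorable zone is empty on one set. A different set or statistic would also explain the report, so it does not settle the matter.
- **The SAP should not show interim CP or p.** Correct: Protocol 12.5.2 restricts them. The governing set and the precedence can be stated without disclosing them.
- **The 4.108% sample-size calculation is an extra interim task.** Correct: the trial itself is sized at 5%. The two levels still need reconciling.
- **Fixed N = 106 is not a written path when the stop comes first.** Correct: the 3.23% (6.5% two-sided) and 0.028 figures are an upper figure and an illustration only.
- **0.04108 is stricter than the named function allows at this look.** True, so that mismatch alone does not inflate error. It is still an incorrect derivation statement.
- **The cited methods may cover early stopping.** This cannot be judged from the documents. The sentence in 12.5.4 speaks only of a sample-size increase.

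**Conclusion.** The concern holds. At 86 of 106 on one set, the Favorable zone (p ≤ 0.0362, or 0.0392 on t) lies inside the stop-for-success zone (p ≤ 0.04108). No precedence is stated, and no governing set is named for the success, Favorable or Promising rules. About 69% of interims under the design assumptions fall in the conflict.

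The final 0.05 test is unsupported as written. It exceeds the stated overall level if the efficacy stop was available (2.6–3.1% one-sided against 2.5%) and is conservative if continuation took precedence (1.8–2.3%).

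These figures assume normal approximations, one analysis set and CP at the observed effect, which is the protocol's definition. With CP at the design effect instead, the 80% cut would be p = 0.0467 and containment would fail. The margin is thin, 2.64 against 2.71 points. Whether the success boundary was met at the actual interim cannot be determined from the documents. This must be fixed before the final analysis.

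**What to change.** 1. Before the treatment code is revealed, the independent statistician records in a dated note the analysis set, test statistic, CP formula, efficacy boundary and precedence in force at the interim, and whether the boundary was binding. Interim Z, p and CP stay sealed. SAP section 6 says the code was unrevealed at SAP finalization; its later status is not documented.
2. The SAP states the final significance level that follows from that record. It is 0.05 only if the record shows that no efficacy claim was available at the interim. Otherwise it is derived for the actual set, information fraction and sample-size path. The readings above span 0.027 to 0.043, so no fixed figure should be adopted without the record.
3. The SAP states that the two zones overlapped and which took precedence, corrects the link between 0.04108 and the Pocock-type function, and reconciles the 4.108% calculation with the 0.05 final test.

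The cost is a short note and a few lines of SAP text. If the final level becomes stricter than 0.05, some power is lost.
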